After the first subject in each cohort completes day 30 (\pm 2 days), subsequent to day 15 dosing of the other 2 subjects in the same cohort, an interim safety evaluation will be performed with the submission of safety data to the Data Safety Monitoring Committee (DSMC). If the DSMC recommends continuing the study, the next dose cohort will be treated. This process will be repeated between the second and third dose cohort and between the third and fourth dose cohort. All 4 dose cohorts will be followed for one year from the time of the first dose of study drug administration. If a dose limiting toxicity is observed in one subject in any dose group, three additional subjects will be added to the dose cohort in which the toxicity was observed. If no additional DLTs are observed in the 6 subjects in this dose level, it will be considered the Maximum Tolerated Dose (MTD). If a DLT occurs in 2/6 subjects, then the preceding dose level will be considered the MTD.

Structure: Single center

Sample Size: Approximately 12-15 subjects

Study Population: Subjects selected for this study will have critical limb ischemia

that has not responded to standard therapy with symptoms

including pain at rest, and/or ischemic ulcers.

Study Assessments: The following assessments will be performed at screening and / or at designated time points throughout the study:

• Informed Consent

- Physical Exam
- Vital Signs
- Pregnancy Test
- Photograph and measurement of ulcer
- Mammogram
- Collection of concomitant medications
- Collection of medical history
- Assessment of CLI
- Collection of adverse events
- Ankle Brachial Index (ABI)
- Toe Brachial Index (TBI)

- Wave Form Analysis
- Transcutaneous Oxygen Pressure Assessment (TcPO₂)
- High resolution MRA
- Visual Analog Scale (VAS) for pain
- Analgesic usage
- Safety Laboratory Testing (Hematology, Chemistry, Urinalysis)
- Retinal fundoscopy
- 12-lead ECG
- Tumor marker testing (Alpha feto-protein, CEA, PSA [males only], CA19-9 & CA125)
- Infection testing (HIV, Hepatitis B, CMV, HTLV, VDRL)
- HGF levels
- Anti-HGF antibody levels
- VM202 DNA levels
- Endothelial progenitor cell assay
- Chest X-ray or CT scan of the chest (if the subject has a previous history of tobacco use, a CT scan will be performed instead of the chest X-ray)

Rationale:

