4.5 Treatments

The test product used in this study is VM202, a plasmid DNA-based therapeutic product expressing HGF. The HGF gene, HGF-X7 is a genomic-cDNA hybrid HGF construct (HGF-X), which expresses both isoforms of HGF with high efficiency. VM202 has been developed using pCK DNA which has been safely used in previous human clinical trials with VEGF as the therapeutic vector. The VM202 plasmid, also identified as pCK-HGFX7 with 7377 base pairs, is composed of a HCMV enhancer/promoter, a growth hormone polyadenylation terminator sequence, ColE1 originator, and the Kanamycin resistance gene, on a pCK backbone.

For each of the 4 cohorts a different dose level will be administered as follows:

Cohort I- 2 mg of VM202

Cohort II- 4 mg of VM202

Cohort III-8 mg of VM202

Cohort IV-16 mg of VM202

In the event that a dose limiting toxicity (DLT) is determined after the safety review between Cohort I and Cohort II, between Cohort II and Cohort III or between Cohort III and Cohort IV, there will be 3 additional subjects treated at the same dose. If a DLT occurs in 2/6 patients, then the preceding dose level will be considered the MTD.

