There will be a mandatory review of all safety data between the treatments of all dose cohorts (Cohorts I-IV). No subject may be enrolled in subsequent cohorts until the DSMC has reviewed the data and provided a written notice to the sponsor that the trial may continue.

In the event that a DLT is determined after the safety review in any cohort, there will be 3 additional subjects treated at the same dose level. If no further DLTs are observed in the 6 subjects and the DSMC approves dose escalation, then subjects can be enrolled to the

next higher dose level. If 2/6 subjects experience a DLT then the preceding dose level will be considered the MTD.

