7.1.9 Dose Limiting Toxicity (DLT)

Dose limiting toxicity will be defined as the occurrence of any of the following:

- Acute anaphylaxis including erythema, hives, wheals, wheezing, stridor or respiratory distress
- Temperature >102°F with negative blood cultures within 24 hours of study drug administration
- Evidence for active tissue necrosis at the injection site within two weeks of study drug administration

Dose limiting toxicities will be recorded on the CRF. In the event of a DLT at any dose, 3 additional subjects will be added to the dose cohort in which the toxicity was observed. If no additional DLTs are observed in the 6 subjects in this dose level, it will be considered the Maximum Tolerated Dose (MTD). If a DLT occurs in 2/6 patients, then the preceding dose level will be considered the MTD.

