3. STUDY OVERVIEW

This is a prospective, dose-escalation single center study to evaluate the safety and tolerability of intramuscular VM202 in subjects with critical limb ischemia.

Subjects selected for this study will have critical limb ischemia that has not responded to standard therapy with symptoms including pain at rest or ischemic ulcers.

The study will consist of four (4) cohorts with a total of 3 subjects enrolled in each cohort to VM202. The cohorts will be based on the planned different amounts of VM202 to be given. Planned levels of VM202 to be administered (defining the 4 cohorts) are the following: 2 mg, 4 mg, 8 mg and 16 mg. For each dose cohort, VM202 will be administered as a local intramuscular injection in 2 divided doses with a 2-week interval between the injections. Preliminary efficacy (hemodynamic assessments), safety and tolerability will be evaluated at Baseline (screening) and at designated time points throughout the study.

After all subjects in the first dose cohort have completed the 30-day (± 2 days) follow-up visit following the 1st dose of study drug, an interim safety evaluation will be performed with the submission of safety data to the Data Safety Monitoring Committee (DSMC). If the DSMC recommends continuing the study, the second dose cohort will be treated. This process will be repeated between the second and third dose cohort and between the third and fourth dose cohort. All 4 dose cohorts will be followed for up to five years from the time of the first dose of study drug administration. If a dose limiting toxicity (DLT) is observed in one subject in any dose group, three additional subjects will be added to the dose cohort in which the toxicity was observed. If no additional DLTs are observed in the 6 subjects in this dose level, it will be considered the maximum tolerated dose (MTD). If a DLT occurs in 2/6 subjects, then the preceding dose level will be considered the MTD.

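### For Cohorts I-III, one DLT in six subjects makes the dose the MTD in the Synopsis, Protocol 7.1.9 and SAP 3, but allows the next higher dose in Protocol 6.1.1, and no passage says which rule governs

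*Protocol*

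**What the plan says.** The Synopsis (Study Design) gives the trigger for expansion of the affected cohort: "If a dose limiting toxicity is observed in one subject in any dose group, three additional subjects will be added". The protocol section on the number of study subjects puts the trigger at 1 of 3 and makes it conditional on a DSMC recommendation to continue.

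For one DLT among the resulting six subjects:

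- Protocol 7.1.9, and the Synopsis in the same words: "If no additional DLTs are observed in the 6 subjects in this dose level, it will be considered the Maximum Tolerated Dose (MTD").
- SAP 3: "If no additional DLTs are observed in the 6 subjects in this dose level, it will be considered the maximum tolerated dose (MTD").
- Protocol 6.1.1: "If no further DLTs are observed in the 6 subjects and the DSMC approves dose escalation, then subjects can be enrolled to the" and, continuing, "next higher dose level. If 2/6 subjects experience a DLT then the preceding dose level will be considered the MTD".

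Protocol 4.5 gives only the other outcome: "If a DLT occurs in 2/6 patients, then the preceding dose level will be considered the MTD". It is silent on 1/6.

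Protocol 6.1.1 also sets the gate between cohorts, which requires DSMC clearance in writing: "No subject may be enrolled in subsequent cohorts until the DSMC has reviewed the data and provided a written notice to the sponsor". Protocol 9.4 says the DSMC works from a Guidance Document and has stopping rules fixed in advance. That document is not among those reviewed. The Synopsis gives the sample size as "Approximately 12-15 subjects".

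**The concern.** At 2, 4 or 8 mg, a single data pattern (1/3, then 0/3) has two stated consequences. In three places it fixes the MTD at the current dose. In a fourth it makes the next higher dose available, subject to DSMC approval. At 16 mg there is no higher dose, so no conflict arises.

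Three things depend on the rule: the escalation question put to the DSMC, the highest dose any subject receives, and the maximum enrolment. The primary objective is safety and tolerability, and dose escalation is the design, so the condition that ends escalation should have one meaning.

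**Working it through.** **1. The passages side by side.**

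| Place | 1 DLT in 6 | 2 DLTs in 6 |
|---|---|---|
| Synopsis | this dose is the MTD | preceding dose is the MTD |
| Protocol 7.1.9 | this dose is the MTD | preceding dose is the MTD |
| SAP 3 | this dose is the MTD | preceding dose is the MTD |
| Protocol 6.1.1 | next dose may open if the DSMC approves | preceding dose is the MTD |
| Protocol 4.5 | not addressed | preceding dose is the MTD |

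All five agree on 2/6. The disagreement is confined to 1/6. Section 6.1.1 uses the term MTD only for 2/6.

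**2. The stated sample size.** With no DLT, 4 × 3 = 12. If 1/6 fixes the MTD and ends escalation, only the last cohort treated can be expanded, so the maximum is 3+3+3+6 = 15. This reproduces 12-15, although the protocol rests the size on feasibility and gives no derivation. Under 6.1.1 every cohort can expand: 6+6+6+6 = 24. If Cohorts I and II closed with three subjects each: 3+3+6+6 = 18.

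**3. How often it would matter.** The documents state no DLT rate, so these are illustrations. Assumptions: independent subjects with one DLT probability p at every dose; expansion after exactly 1/3; two or more DLTs in a cohort end escalation (the documents cover 2/6; its extension to 2/3 and 3/3 is assumed); the DSMC approves whenever the rule permits. With q = 1 − p:

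- a = P(0/3) = q³
- c = P(1/3) = 3pq²
- b = P(1/3, then 0/3) = 3pq⁵

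Only Cohort III open, I and II closed with three each: P(conflict) = b; P(16 mg given) = a if 1/6 is the MTD, a + b under 6.1.1; P(N>15) under 6.1.1 = bc.

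Cohorts I-III all open: P(conflict) = b(1 + a + a²); P(16 mg given) = a³ against (a + b)³; P(N>15) under 6.1.1 = 3a²bc + 3ab² + b²c.

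Example at p = 0.05: a = 0.857, c = 0.135, b = 0.116. With only III open, P(16 mg) is 0.857 against 0.857 + 0.116 = 0.973, and P(N>15) = 0.116 × 0.135 = 0.016. With I-III open, P(conflict) = 0.116 × (1 + 0.857 + 0.735) = 0.301, and P(N>15) = 0.0347 + 0.0347 + 0.0018 = 0.071.

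| Assumed p | 1% | 2% | 5% | 10% |
|---|---|---|---|---|
| **Only III open:** P(conflict) | 2.9% | 5.4% | 11.6% | 17.7% |
| P(16 mg), 1/6 = MTD vs 6.1.1 | 97.0 vs 99.9% | 94.1 vs 99.5% | 85.7 vs 97.3% | 72.9 vs 90.6% |
| P(N>15) under 6.1.1 | 0.1% | 0.3% | 1.6% | 4.3% |
| **I-III open:** P(conflict) | 8.3% | 15.3% | 30.1% | 40.0% |
| P(16 mg), 1/6 = MTD vs 6.1.1 | 91.4 vs 99.6% | 83.4 vs 98.6% | 63.0 vs 92.2% | 38.7 vs 74.4% |
| P(N>15) under 6.1.1 | 0.5% | 1.7% | 7.1% | 14.5% |

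When 1/6 is the MTD, P(N>15) = 0 throughout. The Cohort-III-only rows are the more relevant ones, because the Version 5.0 entries in Appendix E already cite safety shown in the first two cohorts.

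**The case against.** **The texts can be reconciled.** The Synopsis, 7.1.9 and SAP 3 attach a label to the dose; none says that the next cohort may not open. Section 6.1.1 is the only passage on the escalation decision after 1/6, and it leaves that decision to the DSMC. On this view the MTD is provisional until a higher dose has been tried. It stands that a stop is inferred from the label and not written out. But no passage calls the MTD provisional, and 6.1.1 keeps the term for 2/6. In 7.1.9 the same phrase would have to be provisional for 1/6 and final for 2/6 in the next sentence. DSMC approval says who decides, not whether a 1/6 dose is eligible for escalation. The Guidance Document may settle this, but neither protocol nor SAP says that it overrides the MTD rule.

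**The amendment log settles it.** Version 2.0 introduced both wordings and gives the same reason, clarification of the standard 3+3 design, for both. Version 3.0 changed only the 2/6 text. The log ranks neither.

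**Practical exposure is small.** Besides the Version 5.0 remark on the first two cohorts, the Version 6.0 log calls 30 months the actual study duration, so escalation may have been far advanced. The documents do not report cohort status. Protocol 1.3 reports that a product on the same plasmid backbone was well tolerated in nine subjects at 2, 4 or 8 mg, with no attributed serious adverse events. That evidence is thin: the gene differs, serious adverse events are not DLTs, and at a 10% rate no event in nine subjects has probability 0.9⁹ = 0.39. A constant rate over an eightfold dose range is also a simplification. These points limit the size; the textual conflict needs none of the percentages.

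**The documents are not neutral.** This stands. Three of the four passages, and the stated 12-15 subjects, fit 1/6 as the MTD. It supports a default but does not remove the contrary sentence in 6.1.1.

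**Conclusion.** The inconsistency is real and lies in current text: for Cohorts I-III, the consequence of 1/6 depends on which section is read. It should be fixed, as a wording correction of moderate weight. It affects the DSMC decision, the top dose and maximum enrolment (15 against 24, or 18). For assumed constant DLT rates of 1% to 10%, it arises with probability 3% to 18% if only Cohort III is open, and 8% to 40% if Cohorts I-III are.

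Stronger readings that a reader might infer are not supported:

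- *A site could escalate past an MTD by itself.* Protocol 6.1.1 requires DSMC review and written notice first.
- *The analysis is compromised.* The MTD is not an objective or endpoint, and no SAP table or listing reports it.
- *Enrolment beyond 15 breaches the plan, or 24 is to be expected.* The Synopsis figure is approximate, and 24 has probability b³c, or 0.02% at a 5% rate and 0.14% at 10%.

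**What to change.** State one 1/6 rule in identical words in the Synopsis, Protocol 6.1.1, Protocol 7.1.9 and SAP 3, add it to Protocol 4.5, and align it with the DSMC stopping rules referred to in 9.4.

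- **(a) Default, because it fits the stated sample size.** Keep 1/6 as the MTD, state that escalation ends there, and delete the escalation sentence in 6.1.1. The 12-15 figure stays. The cost is a lower chance of testing 16 mg: 86% against 97% at an assumed 5% rate with only Cohort III open.
- **(b) If the sponsor and DSMC intend escalation after 1/6.** Remove the MTD label for that outcome in Cohorts I-III, keep the DSMC condition, and restate maximum enrolment as up to 24 (18 if Cohorts I and II closed with three each). The cost is a larger stated maximum, and more subjects may receive a higher dose after a DLT at a lower one.

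Either way only wording changes. Section 7.1.9 triggers expansion after a DLT at any dose, which is looser than the 1 of 3 given under the number of study subjects. Leave that wording alone unless an explicit rule for two or more DLTs in the first three subjects is added with it; narrowing the trigger by itself would leave 7.1.9 with no action for 2/3 or 3/3.

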7.2 Efficacy

7.2.1 Hemodynamic Assessments

7.2.1.1 Ankle-Brachial Index (ABI)

Ankle-Brachial index will be obtained using standard, calibrated instruments as described in Appendix B. The pressure in both arms with be measured, and the higher of the two pressures will be used. All values will be recorded at each assessment in the Case Report Form.

7.2.1.2 Toe-Brachial Index (TBI)

Toe-Brachial index will be obtained using standard, calibrated instruments as described in Appendix B. The pressure in both arms with be measured, and the higher of the two pressures will be used. All values will be recorded at each assessment in the Case Report Form.

7.2.1.3 Wave Form Analysis (PVR)

A copy of the arterial flow wave form will be obtained at each assessment. This will be placed in the subject's record and sent for analysis at the end of the study.

7.2.1.4 Transcutaneous Oxygen Pressure Assessment (TcPO₂₎

During the screening period the TcPO₂ will be measured at pre-defined locations on the anterior and posterior calf and dorsum of the foot. The limb/chest TcPO₂ index will be calculated by using the lesser of the lower limb measurements. Transcutaneous oxygen pressure methodology is instrument dependent and therefore the investigator will follow the standard procedures defined by their instrument's manufacturer and the written instructions provided by the Sponsor to standardize this procedure.

At multiple time points prior to and after treatment (Days 1, 15, 28, 59, 91, 180 and 365), the subject will have TcPO₂ measured at pre-defined locations on the anterior and posterior calf and dorsum of the foot. For analysis purposed, it is important that placement of the sensor used for the TcPO₂ measurement is always on the same pre-defined limb locations for screening and follow-up visits unless it is not possible (site amputated, areas of ulceration/gangrene). Marking the site with indelible ink is recommended. If a sensor placement site is unavailable due to amputation or areas of ulceration/gangrene, sensor placement site will be assigned a clinically equivalent default

TcPO₂ value of zero pressure ("0 mmHg"). Hard copy instrumentation printout will be included in the source documentation to support the TcPO₂ data.

7.2.2 High Resolution MRA

Subjects will have High Resolution MRA at Baseline and at 3 months and 6 months post-treatment. Area of Ischemic Ulcer (Digital Photography and Ulcer Measurement)

If one or more ischemic ulcer is present on the subject's studied limb, a digital photograph will be taken of the largest contiguous area of ulceration with a target plate included in the image for calibration purposes. The wound perimeter will be traced and the area of ulceration will be calculated in square millimeters. If a MRA can not be done, a CT-Angio (CTA) can be performed on the subject.

7.2.3 Pain VAS Score

Pain intensity will be assessed by subjects marking a place on a 100 mm visual analog scale ranging from 0=no pain to 100=worst possible pain as described in Appendix C. The distance from 0 to the mark will be measured in millimeters (0 to 100) and recorded on the CRF as the VAS score.

7.2.4 Subject Analgesic Use

Analgesic use including generic name, dose and frequency will be collected at Baseline and each subsequent visit and will be recorded on the CRF. Any change from in the dose level or frequency of analgesics used will be documented.

8.0 Adverse Events and Serious Adverse Events

8.1 Adverse Event Definition

An AE is the development of an undesirable medical condition or the deterioration of a pre-existing medical condition following or during exposure to a pharmaceutical product, whether or not considered causally related to the product. AEs will be graded according to the National Cancer Institute's Common Terminology for Adverse Events v3.0 criteria.

An undesirable medical condition can be symptoms (e.g., nausea, chest pain), signs (e.g., tachycardia, enlarged liver) or abnormal results of an investigation (e.g., laboratory findings, electrocardiogram).

Therefore, an AE would include the following:

- Any event that is new (i.e., was not seen prior to the start of the study).
- A condition detected or diagnosed after the trial medication administration, even though it may have been present prior to the start of the study.
- A pre-existing intermittent event or condition that recurs with increased intensity and/or frequency after the start of the study.
- A pre- or post-treatment event that results from study participation (i.e., invasive procedures, modification of subject's therapeutic regimen)
- A change in blood pressure or heart rate that results in discontinuation of dosage or that exceeds protocol-specified criteria

An AE does not include the following:

- The disease or disorder being studied, or a sign or symptom of that disease or disorder, unless it is more severe than expected for the subject's condition.
- An overdose of the study medication if the subject is asymptomatic.
- A medical or surgical procedure (e.g., surgery, endoscopy, tooth extraction).
 Depending on the trial design, such a procedure may be the result of an AE or may result in an AE, but is not an AE itself.
- A pre-existing condition or disease that does not worsen following study drug administration.
- Hospitalization for elective surgery for a pre-existing disease or condition that did not worsen or for cosmetic surgery.

In this study an AE can include an undesirable medical condition occurring at any time after screening procedures have been started until the final follow-up visit, even if no study treatment has been administered.

When an adverse event occurs, the Investigator must:

- 1. assess whether or not the test article caused the AE;
- 2. determine the intensity of the AE;
- 3. record the action taken regarding the test article;
- 4. indicate whether the AE led to discontinuation of the subject from the study; and
- 5. determine if the AE is serious.

All AEs that occur in any subject enrolled, before treatment, during treatment, or up to and including study Day 365 whether or not related to the study drug, must be recorded on the appropriate CRF form provided.

The following are definitions of levels of severity:

- Mild: an awareness of symptoms but easily tolerated
- Moderate: symptoms interfering with daily activities
- Severe: incapacitating, with inability to perform normal daily activities.

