1.0 Background Information

1.1 Peripheral Artery Disease

Peripheral arterial disease (PAD) is a common disorder usually caused by atherosclerotic changes in the arteries supplying the lower extremities, resulting in ischemic limb disease. Clinical manifestations of lower extremity PAD are related to the severity of muscular ischemia, which depends on the degree of arterial stenosis. Intermittent claudication is a common, initial presentation. Critical limb ischemia denotes a condition of severe arterial obstruction due to advanced PAD, associated with breakdown of the skin or pain in the lower limb at rest (Appendix A). The natural history of critical limb ischemia has been well documented to have an inexorable downhill course, frequently leading to the amputation of the affected limb. Two main etiologies of PAD are known as atherosclerotic peripheral arterial disease and thromboangiitis obliterans (Buerger's disease).

Bypass surgery can be recommended for subjects with critical leg ischemia if the arterial circulation of the lower calf or foot includes a reconstituted artery, the outcomes of surgery involving small-size arteries are often unsatisfactory due to a high failure rate. Many subjects face amputation of their limb as the sole therapeutic option for the severe symptoms of critical limb ischemia, when PTA or bypass surgery fails to improve the symptoms. Psychological testing of such subjects typically shows quality-of-life indices similar to those of subjects with terminal cancer. It is estimated that about 150,000 subjects per year require lower-limb amputations for ischemic diseases in the United States alone (corresponding statistics is not available in Korea). Their prognosis after amputation is even worse. The perioperative mortality for below-knee amputation is 5 to 10 percent and for above-knee amputation 15 to 20%. Moreover, full mobility is achieved in only 50% of below-knee and 25% of above-knee amputees. These forbidding statistics result from the lack of efficacious drug therapy for PAD. Consequently, there is an urgent need for novel treatment strategies for subjects with critical limb ischemia.

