6.4.4 Peripheral Vascular Procedures

The performance of any peripheral vascular procedures, including, but not limited to, peripheral bypass surgery, peripheral endarterectomy, peripheral angioplasty or amputation, are events that may occur during the course of the study. The Investigator will document all peripheral vascular interventions performed during the study period.

If the subject reports the occurrence of any disease-related events (e.g., amputation, revascularization bypass, angioplasty), every effort must be made to bring the subject back to the study site for full documentation of the event including sufficient information from the subject, hospital, any treating physician for each peripheral vascular procedure. This information is required by the Sponsor and will be added to the SAE CRF. Information will include:

- Date of intervention
- Type of intervention (e.g., PTA, peripheral bypass, amputation)
- Surgical location (e.g., iliac, femoro-popliteal, infra-popliteal; amputation: AKA BKA)
- Surgical materials (e.g., PTFE, HUV, Dacron)

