8.2 Definition of an SAE

For each AE, you must determine if it is a serious adverse event (SAE) according to the following definition.

An SAE is an AE, occurring at any dose, which fulfills one or more of the following criteria:

- An event that results in death.
- An event that is immediately life threatening. This does not include an event that, had it occurred in a more serious form, might have caused death.
- An event that results in persistent or significant disability or incapacity.
- An event that is a congenital abnormality/birth defect
- An event that requires in-subject hospitalization or prolongs an existing
 hospitalization. Complications that occur during hospitalization and do not meet
 at least one of the above criteria for seriousness are AEs, not SAEs.
 Hospitalization means that the subject was formally admitted to the hospital, and
 does not include presentation at an emergency room.
- An event that, though not included in the above list, is an important medical event that may jeopardize the safety of the subject or may require medical or surgical intervention to prevent one of the outcomes listed above.

Medical and scientific judgment will be exercised in deciding whether a case is serious in those situations where important medical events may not be immediately life threatening or result in death, hospitalization, disability or incapacity. These include events that may jeopardize the subject or may require medical or surgical intervention to prevent one or

more outcomes listed in the definition of serious. Such events will usually be considered as serious. Examples of such events are:

- Angioedema not severe enough to require intubation but requiring intravenous hydrocortisone treatment
- Hepatotoxicity caused by paracetamol (acetaminophen) overdose requiring treatment with N-acetylcysteine
- Intensive treatment at the study site, in an emergency room, or at home for allergic bronchospasm
- Blood dyscrasias (e.g., neutropenia or anemia requiring blood transfusion) or convulsions that do not result in hospitalization
- Development of drug dependency or drug abuse (e.g., analgesics).

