7. DEMOGRAPHIC AND BASELINE CHARACTERISTICS

Demographic variables include: age, sex, ethnicity, race. Medical history and peripheral vascular disease intervention history at baseline will also be considered. Demographic and baseline characteristics will be summarized for the Safety and ITT analysis populations.

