10.2 Adverse Events

All adverse event summaries will be restricted to Treatment Emergent Adverse Events (TEAE), which are defined as those AEs that occurred after dosing and those existing AEs that worsened during the study. Verbatim terms on case report forms will be mapped to preferred terms and system organ classes using the MedDRA dictionary (version 9.1).

Each adverse event summary will be displayed by dose cohort. Summaries that are displayed by system organ class and preferred terms will be ordered by descending order of incidence of system organ class and preferred term within each system organ class. Summaries of the following types will be presented:

- Subject incidence of TEAEs and total number of unique TEAEs by MedDRA system organ class and preferred term;
- Subject incidence of TEAEs by MedDRA system organ class, preferred term, and highest severity. At each level of subject summarization a subject is classified according to the highest severity if the subject reported one or more events. AEs with missing severity will be considered severe for this summary;

- Subject incidence of TEAEs by MedDRA system organ class, preferred term, and closest relationship to study drug (Related/Not Related). At each level of subject summarization a subject is classified according to the closest relationship if the subject reported one or more events. AEs with a missing relationship will be considered related for this summary;
- Subject incidence of serious TEAEs and total number of unique serious TEAEs by MedDRA system organ class and preferred term.

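### Protocol 8.1/8.2 and 6.4.4/6.2.12 give different rules for recording an on-study amputation or revascularization, and the SAP has no output designed to count these events by cohort

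*Protocol*

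**What the plan says.** Protocol 4.1.1 makes the incidence of adverse events through Day 365 the first primary safety endpoint. These provisions decide whether a limb procedure counts towards it:

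- **Protocol 8.1, exclusions from the AE definition.** One is "The disease or disorder being studied, or a sign or symptom of that disease or disorder, unless it is more severe than expected", judged against the subject's own condition. Another is any medical or surgical procedure: "such a procedure may be the result of an AE or may result in an AE, but is not an AE itself".
- **Protocol 8.2.** "An SAE is an AE, occurring at any dose, which fulfills one or more of the following criteria".
- **Protocol 6.4.4.** This covers bypass, endarterectomy, angioplasty and amputation during the study, and describes such events as disease-related. It asks for date, type, surgical location and materials: "This information is required by the Sponsor and will be added to the SAE CRF".
- **Protocol 6.2.12.** Bypass, angioplasty and amputation in follow-up are named alongside SAEs and are to be reported immediately.
- **Protocol 5.4 and 6.4.2.** The first discontinues from the study a subject who needs an intervention for acute limb ischemia. The second withdraws from treatment a subject who needs an intervention for limb ischemia, but keeps in the study anyone who has received a dose.
- **SAP 7.** "Medical history and peripheral vascular disease intervention history at baseline will also be considered". This is the subject of Table 4 and Listing 5.
- **SAP 10.2.** "All adverse event summaries will be restricted to Treatment Emergent Adverse Events (TEAE").
- **SAP 8.1.** The efficacy variables include no amputation or revascularization variable.

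**The concern.** The two 8.1 exclusions work together. The procedure is not an AE, and the worsening that led to it is an AE only if the investigator judges it to exceed what was expected for that subject. Protocol 1.1 describes critical limb ischemia as "frequently leading to the amputation of the affected limb", so an investigator could fairly call progression to amputation expected. By 8.2 it would then not be an SAE either. An investigator who starts from 6.4.4 puts the same event on the SAE form.

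Two sites, or one site on two occasions, could thus treat identical events differently without breaking the protocol. Limb loss is a serious outcome in a first study of a product injected into an ischemic limb. The plan also foresees it: 7.2.1.4 assigns a TcPO₂ of zero to a sensor site lost to amputation, and the Rationale hopes for a lower need for amputation.

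**Working it through.** The plan states no rate, power or other figure on this point, so there is nothing to reproduce. The check is a trace through the text, followed by simple arithmetic.

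**Step 1. One event under each set of rules.** Take a dosed subject whose treated limb worsens and is amputated.

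- *Following 8.1 and 8.2:* the amputation is a procedure, so it is not an AE. The worsening is the disease under study. If it is judged expected for that subject, it is not an AE and so cannot be an SAE. Contribution to AE incidence: 0.
- *Following 6.4.4 and 6.2.12:* details go on the SAE form and the event is reported immediately. If it is handled as an SAE, 8.5 also requires an entry on the AE page. Contribution: 1.

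The general definition in 8.1 counts deterioration of a pre-existing condition as an AE. That favors recording the worsening, but the disease exclusion qualifies it and no text says which prevails.

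**Step 2. Where the event could appear in the SAP outputs.**

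| Output | Does it capture an on-study limb procedure? |
|---|---|
| Table 4, Listing 5 | No; intervention history at baseline |
| Table 1 | Only as the primary reason for discontinuation. One row is specific to acute limb ischemia; the AE, investigator-decision and other rows could take further cases. Under 6.4.2 a dosed subject may stay in and enter no row |
| Tables 12-15, Listings 15-16 | Only if accepted as an AE or SAE |
| Table 18 (Extremities), Listings 9 and 20 | Limb status at visits; no count of procedures |
| Efficacy tables | No limb-event variable |

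None of the 31 listings in Appendix A is for on-study procedures.

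**Step 3. Size.** Planned numbers: 4 cohorts × 3 = 12, and 12 + 3 = 15 with one expanded cohort, matching the stated 12-15. Exact (Clopper-Pearson) 95% intervals:

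- Cohort of 3: 0/3 = 0% (0 to 71%); 1/3 = 33% (1 to 91%).
- Whole trial of 12: 0/12 = 0% (0 to 26.5%); 1/12 = 8% (0.2 to 38.5%).

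How likely the issue is to arise depends on a rate that the documents do not give. Assuming a one-year risk p per subject, P(at least one event in 12) = 1 − (1 − p)^12 and the expected number is 12p:

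| Assumed p | P(at least one in 12) | Expected in 12 |
|---|---|---|
| 5% | 0.46 | 0.6 |
| 10% | 0.72 | 1.2 |
| 20% | 0.93 | 2.4 |
| 30% | 0.99 | 3.6 |
| 40% | 0.998 | 4.8 |

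The last column is a ceiling on how many subjects could be recorded differently. It would be reached only if every event were classified differently under the two readings.

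**The case against.** The strongest reply is that the protocol already points one way. 8.1 removes the procedure, not the condition behind it. Its severity test is relative to the individual subject, and entry requires 30 days of stable symptoms and excludes anyone who will need amputation within 4 weeks, so limb loss is not plainly expected in an enrolled subject. Worsening accepted as an AE becomes serious under 8.2 if it leads to hospitalization or disability, and 8.5 asks for the diagnosis as the term. The amendment log gives the purpose of the 6.4.4 sentence, which is still in force, as clarifying how these procedures are captured as SAEs.

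On outputs, SAP 4 promises by-subject listings of CRF data, which matter greatly with 12-15 subjects. Table 18 shows changes in the extremities whatever the AE status. Subjects are also selected as unsuitable for bypass or angioplasty, so the documents give little reason to expect many revascularizations.

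Much of this stands. Many events would probably reach Table 15 and Listing 16, and intent favors SAE capture. But intent is not written into 8.1, which has no exception or cross-reference, and the severity test remains a case-by-case judgment. Table 18 is a weak substitute: subjects enter with rest pain or ulcers, so the extremities may already be abnormal at screening and show no shift.

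**Conclusion.** The point holds. The protocol gives two unreconciled rules for recording on-study amputation and revascularization, and no SAP table or listing is designed to count these events. An event may therefore not be counted by cohort. The size is one subject at a time, 0/3 against 1/3 in a cohort. That step rests on the planned cohort size alone; the likelihood of meeting it rests on assumed rates.

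Three stronger readings are tempting, and the documents do not support them. A reader might infer that these events would be absent from every result. They would not necessarily be: an event handled as an SAE should reach Table 15 and Listing 16, and Tables 1 and 18 and Listing 9 offer partial routes. A reader might take limb loss as the trial's main progression outcome, but neither document makes it an endpoint. A reader might also take 1.2 to 4.8 of 12 subjects (10 to 40% risk) as the number misrecorded. That is a ceiling under an assumed rate.

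**What to change.** 1. **Protocol.** Reconcile 8.1 and 8.2 with 6.4.4 and 6.2.12 so that one recording rule covers amputation and peripheral revascularization after the first dose, with the underlying condition as the event term. A sentence in 8.1 with cross-references would do. Also reconcile 5.4 with 6.4.2 on whether a dosed subject who has an intervention stays in the study, because that decides what Table 1 can show.
2. **SAP.** Add one Safety-population table and one listing, independent of AE status. By cohort through Day 365, give the number of subjects with amputation (by level), with bypass or PTA, and with any of these, with day of event and limb (treated or other). Section 6.4.4 also names endarterectomy, so the combined row should include it.

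The cost is one sentence, one table and one listing. Date, type and location are already required by 6.4.4. Limb side is not listed there, and its amputation examples are above and below the knee only, so limb side and minor-amputation level may need adding to the CRF. The downside is a slightly higher SAE count from disease-related events.
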